MFGM is a unique milk fat-derived antiinflammatory constituent. The MFGM is the membrane (trilayer) surrounding secreted milk fat droplets.¹⁰ It originates from the apical surface of mammary epithelial cells and is comprised of a unique triple phospholipid and cholesterol layer embedded with proteins and glycoproteins. The genes that synthesize MFGM are conserved across species and its composition differs little between-species. Notably, phospholipids account for 1% of total milk lipid, with ~one-third each from sphingomyelins, phosphatidylcholines, and phosphatidylethanolamines. Although MFGM is present in most dairy foods, churn buttermilk is quite rich in this membrane fraction. Indeed, churning of milk fat disrupts the membrane surrounding the fat globules. This results in the coalescence of free fat that ultimately yields butter. In contrast, buttermilk is the aqueous phase (i.e. MFGM-containing portion). MFGM constituents (e.g. polar lipids, gangliosides, proteins) improve intestinal health⁹ and exert antiinflammatory activity systemically and at the gut.¹¹⁻¹⁴

MFGM protects against endotoxin-induced gut permeability. MetS is characterized by increased “gut leakiness” consistent with our preclinical studies in obese mice showing that endotoxemia occurs in association with decreased expression of intestinal tight junction proteins (e.g. occludin, zonula occluden, claudin).^{15,16} In contrast, our dietary interventions with a functional food (green tea) fully protected against the loss of gut barrier integrity and normalized serum endotoxin levels to attenuate hepatic TLR4/NF κ B inflammation and oxidative stress.^{15,16} Similarly, the polar lipids present in MFGM provide resistance to epithelia stress.^{12,17-19} These bioactivities are important, because they are expected to support MFGM to alleviate metabolic endotoxemia in the proposed clinical nutrition intervention, consistent with a mechanism of improving gut barrier integrity (*Obj 1*) and attenuating TLR4/NF κ B inflammation and glucose intolerance (*Obj 2*).

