Blood Chemistries. Fasting plasma glucose and lipids (total cholesterol, HDL-C, triglyceride) will be measured by clinical assay (Pointe Scientific) at screening, day 0, and day 14. Fasting insulin will be measured by ELISA (ALPCO) at day 0 and day 14. TLR4/NF κ B-dependent genes from isolated peripheral blood mononuclear cells (PMBCs) will be assessed. For each arm of the study, we will measure circulating glucose and insulin at 0, 30, 60, 90, 120, 150, and 180 min following the ingestion of the glucose beverage. TLR4/NF κ B-dependent genes will be assessed from PMBCs at 0 h and 3 h.

Breath Analysis. Breath samples will be collected using a sterile, single use mouth piece into a sterile breath collection bag. Participants will be instructed not to brush their teeth with toothpaste, gargle with mouthwash, chew gum or eat any mints the morning of each test. Breath samples will be analyzed within one hour using a mass spectrometry-based breath analysis technique.

Preparation of Milk Beverages.

Isolation of MFGM Phospholipids. The main component for our formulation, the MFGM containing ingredient (i.e. buttermilk powder), will be prepared as described.⁵² Sweet cream will be prepared from milk obtained from the OSU Waterman Dairy Farm using a cream separator after pasteurization. After tempering (16 h, 4°C), cream is churned using a continuous pilot scale butter churn, and butter fines are then removed by filtration. A pilot plant-scale system using two spiral polymeric membranes fitted in parallel on the module (10 kDa, 11.33 m² total surface area) will be used to concentrate buttermilk. This is performed at 15°C with transmembrane pressure of 500 kPa. Ultrafiltration is performed until a 10-fold volumetric concentration factor is achieved. Diafiltration (DF) is then performed by adding water continuously at 15°C to the feed tank to replace the removed permeate until a 5-fold DF factor is achieved. The final retentate is then spray-dried to obtain buttermilk powder having ~20-40 times the phospholipid content found in commercial milk.

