MFGM and Coconut/Palm Oil Beverages. Our approach entails formulating MFGM- and coconut/palm oil-enriched milks with 10-times the normal concentration of total phospholipids. MFGM (isolated above as buttermilk powder) contains ~2 g of phospholipid per 10 g of solid. Based on commercial whole milk containing 0.2-0.3 g/L phospholipid, the addition of 5-10 g MFGM (i.e. buttermilk powder) would yield a final concentration of 2-3 g/L of total phospholipid in our formulated beverage. Thus, milk beverage manufacture, based on our in-house pilot tests, would be as follows:

MFGM Milk. A modified cream with milk phospholipids will be prepared using 40% butter fat, 10% MFGM ingredient (i.e. buttermilk powder), and 50% skim milk. Ingredients will be homogenized and added to skim milk to prepare milk containing 3.5% total fat (w/w).

Coconut and Palm Oil Milk. A modified cream will be prepared by homogenizing 12.5% coconut oil, 37.5% palm oil, and 50% skim milk. This will yield a milk beverage matched to MFGM milk for

saturated fatty acids, monounsaturated fatty acids, and polyunsaturated fatty acids, but not enriched with phospholipids.

Both beverages will be homogenized (2-stage at 1500 and 500 psi), pasteurized, bottled in single-use servings under aseptic conditions, and refrigerated until use. We anticipate preparing up to 250 gallons of milk beverages to complete the study. Beverages are shelf-stable for 21 d and will be prepared in sufficient volume on a weekly basis proportional to the number of participants enrolled. Phospholipid content will be verified in the [name] Lab to be $\pm 5\%$ of expected concentrations with each prepared batch. Under the aforementioned manufacturing conditions, the energy and nutrient content of both beverages will be matched (3.2% protein and 3.5% fat, *w/w*). However, the MFGM beverage will contain 3 g/L MFGM phospholipid. The coconut/palm oil-based beverage will contain negligible levels of MFGM phospholipids (0.005% *w/w*), reflecting that skim milk is not fully devoid of these polar lipids.

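### At the stated powder strength of about 20% phospholipid, the MFGM milk recipe gives about 1.7-1.85 g/L, not the stated 3 g/L

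*Combined protocol and SAP*

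**What the plan says.** All the figures needed are in the combined protocol and SAP, mostly in section III.C under Preparation of Milk Beverages (MFGM and Coconut/Palm Oil Beverages; MFGM Milk).

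- Powder strength: the MFGM ingredient "contains ~2 g of phospholipid per 10 g of solid".
- Recipe: the modified cream "will be prepared using 40% butter fat, 10% MFGM ingredient (i.e. buttermilk powder), and 50% skim milk".
- Dilution: the cream is "added to skim milk to prepare milk containing 3.5% total fat (w/w").
- Stated result: "the MFGM beverage will contain 3 g/L MFGM phospholipid".
- A separate statement on the amount of powder: "the addition of 5-10 g MFGM (i.e. buttermilk powder) would yield a final concentration of 2-3 g/L of total phospholipid". No denominator is given for the 5-10 g.
- Reference level: commercial whole milk is put at 0.2-0.3 g/L, so ten times that is 2-3 g/L. The section Significance of the Research and Potential Benefits also gives the dose as ten times that of whole milk.
- Control milk: 0.005% w/w phospholipid, attributed to the skim milk.
- Batch check: phospholipid is to be within 5% "of expected concentrations with each prepared batch".
- In section II, "phospholipids account for 1% of total milk lipid". This matters only for one of the favourable readings tested below.

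**The concern.** The phospholipid concentration is the dose of the only active intervention. Powder strength, cream composition and final fat content together fix that concentration, so the recipe and the 3 g/L can be checked against each other. If they disagree, a kitchen cannot follow both, and a reader who wants to repeat the trial or compare doses across studies cannot tell which one defines the product. Three servings a day at an assumed 200-250 mL each is 0.60-0.75 L/d. On that volume the recipe implies about 1.0-1.4 g/d (1.67 x 0.60 to 1.85 x 0.75), and 3 g/L implies 1.8-2.25 g/d.

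**Working it through.** **The plan's own target.** 10 x 0.2-0.3 g/L = 2-3 g/L. The stated 3 g/L is the top of that range. As a multiple of whole milk it reproduces; the question is whether the recipe delivers it.

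**Inputs from the protocol.** Cream fat 40%; powder 10% of cream; powder strength p = 0.20 g/g; final fat 3.5% w/w; skim-milk phospholipid 0.05 g/kg (0.005% w/w). **Assumed:** milk density 1.00-1.03 kg/L.

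**Recipe, upper end (butter fat is the only fat; skim milk credited; density 1.03).**
- Cream share = 3.5/40 = 8.75% of the milk, or 87.5 g/kg
- Powder = 10% x 87.5 = 8.75 g/kg
- Phospholipid from powder = 8.75 x 0.20 = 1.75 g/kg
- Skim milk makes up 1 - 0.0875/2 = 0.956 of the milk and adds 0.956 x 0.05 = 0.048 g/kg
- Total 1.80 g/kg x 1.03 = 1.85 g/L

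**Recipe, lower end (powder phospholipid counted as fat; no skim contribution; density 1.00).**
- Cream share = 3.5/42 = 8.33%; powder 8.33 g/kg; 8.33 x 0.20 = 1.67 g/L

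**Shortfall.**
- Against 3 g/L: 1 - 1.85/3 = 38% to 1 - 1.67/3 = 44%
- Against 2 g/L: 1 - 1.852/2 = 7% to 1 - 1.667/2 = 17%
- As a multiple of whole milk: 1.67/0.3 = 5.6 to 1.85/0.2 = 9.3

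**Could rounding of the powder strength explain it?** If 3 g/L is the expected value, the 5% tolerance has a floor of 0.95 x 3 = 2.85 g/L. The strength needed is (2.85/1.03 - 0.048)/8.75 = 0.31 g/g, rising to 0.35 with phospholipid counted as fat at density 1.00. If the approximate 0.20 is taken to span 0.15-0.25 (an assumption), the recipe gives 1.27-2.30 g/L.

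**Favourable readings at p = 0.20** (skim credited, density 1.00-1.03).

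| Reading | Result (g/L) |
|---|---|
| Butter fat also carries 1% phospholipid (35 g/kg x 1% = 0.35 g/kg) | 2.15-2.21 |
| The 40% is butter at an assumed 80% fat: 3.5/32 = 10.94%, so 10.94 g powder/kg; 2.19 + 0.047 = 2.235 g/kg | 2.24-2.30 |
| Both together: 2.235 + 0.35 = 2.585 g/kg | 2.59-2.66 |

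With both together, 3 g/L needs p = (3/1.03 - 0.397)/10.94 = 0.230, or (3 - 0.397)/10.94 = 0.238 at density 1.00.

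**The 5-10 g sentence.**
- Per litre (assumed): 5 x 0.20 = 1.0 g/L to 10 x 0.20 = 2.0 g/L, or at most 2.3 g/L on a whole-milk base of 0.3 g/L. The claimed yield is 2-3 g/L.
- Per day over 0.60-0.75 L (assumed): 5 g gives 1.0/0.75 = 1.3 to 1.0/0.60 = 1.7 g/L; 10 g gives 2.0/0.75 = 2.7 to 2.0/0.60 = 3.3 g/L.
- The recipe does not settle which is meant. Its 8.33 to 9.0 g/L of powder (8.75 x 1.03 = 9.0) lies inside 5-10 g per litre. Over 0.60-0.75 L it is 5.0-6.8 g per day (8.33 x 0.60 to 9.0 x 0.75), which also lies inside 5-10 g.

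**The case against.** The best reply has four parts.

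First, the powder strength is only approximate, and the recipe is introduced as resting on in-house pilot tests, so the printed percentages may be rounded summaries of something that worked. This stands in part: 3 g/L is not impossible. It can be reached at about 0.23-0.24 g/g if the butter reading and the native phospholipid are both granted. But neither reading is stated in the recipe, no assayed pilot concentration is printed, and the recipe as written needs 0.31-0.35 g/g even to reach 2.85 g/L. That is more than rounding of 0.20.

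Second, the 5-10 g sentence has no denominator. This stands. Per litre is the natural reading because the yield is in g/L, but a daily amount could reach about 3 g/L at the nominal strength. The sentence therefore cannot serve as independent proof of an error. The recipe result does not depend on it.

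Third, 3 g/L is the top of the protocol's own 2-3 g/L range, and against 2 g/L the gap is modest. This is true and belongs in the account of size, but the protocol commits the beverage to 3 g/L, and the recipe as written misses 2 g/L as well.

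Fourth, every batch is assayed to within 5%, and the powder fraction is the obvious thing to adjust. The assay is a real safeguard: if 3 g/L is its target, a batch made to the nominal recipe would fail and the conflict would surface. It would not say whether the recipe or the concentration governs.

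A reader might infer from the arithmetic that participants were under-dosed. The documents do not support that. They give a plan with an approximate strength and a batch check, and no assayed concentration of any batch.

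**Conclusion.** The recipe and the stated 3 g/L do not agree at the printed inputs. The recipe gives about 1.7-1.85 g/L, which is 38-44% below 3 g/L and 7-17% below the 2 g/L end of the ten-times range. This rests on the printed strength of about 0.20 g/g and an assumed density of 1.00-1.03 kg/L; density has little effect. The most favourable combination of readings tested gives about 2.7 g/L at that strength. The shortfall in the 5-10 g sentence (1.0-2.3 g/L against 2-3 g/L) holds only if the amount is per litre.

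The point is minor. It would be wrong to read it as a threat to the trial's validity. The sample-size calculation does not use the phospholipid dose, and the primary outcome and the randomised comparison are unchanged. Even at the recipe's 1.80 g/kg, the MFGM milk has about 1.80/0.05 = 36 times the phospholipid of the control. What is lost is a reproducible statement of the dose.

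**What to change.** Assay the powder before the first batch, using the phospholipid measurement already planned, and then choose one of two routes.

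- **(a) Keep 3 g/L and set the powder from the assay.** At 0.20 g/g this is (3/1.03 - 0.048)/0.20 = 14.3 to 3/0.20 = 15 g powder per kg milk. As a share of the cream it is 14.3/87.5 = 16%, up to 19% with phospholipid counted as fat: at 18.75% powder the cream share is 3.5/(40 + 0.2 x 18.75) = 8.0%, and 8.0% x 18.75% = 15 g/kg. Recheck the 3.2% protein match, because the non-phospholipid powder solids rise from 8.75 x 0.8 = 7 g/kg to about 11.5-12 g/kg.
- **(b) Keep the 10% recipe and restate the dose.** Give the beverage concentration, and its multiple of whole milk, from the assayed strength (about 1.8 g/L if it proves to be 0.20).

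In either case, state the denominator of the 5-10 g, correct the yield if it is per litre, and name the chosen concentration as the target of the 5% batch check. Which concentration is right is for the investigators to decide. The cost is one powder assay, one recalculation and a few words of protocol text; route (a) adds the protein check.

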Summary. This overview demonstrates that: 1) low-grade inflammation in MetS is attributed to endotoxemia in association with poor gut barrier integrity, 2) endotoxemia is causally-related to the initiation of obesity and insulin resistance³⁵ and circulating endotoxin is prognostic of progressive liver function deterioration,³⁶ 3) MFGM constituents provide antiinflammatory and prebiotic activity at the gut and attenuate endotoxemia, and 4) increased SCFAs from commensal bacteria of the gut not only improve gut integrity, but also promote intestinal incretin secretion to help manage glucose intolerance. Thus, our translational studies in MetS persons are expected to provide novel evidence that MFGM exhibits antiinflammatory activity to enhance glucose tolerance by attenuating endotoxemia. These findings would be of *significance* to public health because could they help to establish that dietary fat "quantity" is not necessarily detrimental to MetS risk, but rather fat "quality" potentiates host health due to enhanced gut barrier function. This would lead to evidence-based recommendations to help reverse course of dietary trends indicating that dairy consumption decreases in an age-dependent manner and that ~90% of Americans fail to meet the daily recommended intake of dairy.³

Anticipated Results

We expect the intervention to result in high compliance (>95%), consistent with our rigorous approach to provide all foods and test beverages.

In *Obj 1*, MFGM is *expected* to time-dependently decrease serum endotoxin (i.e. d 0 to d 14), and lower day 14 endotoxin compared with coconut and palm oil-enriched milk. MFGM will also attenuate meal challenge-induced increases in gut-derived endotoxemia. These benefits will correlate with improved gut barrier function as indicated by: 1) decreased urinary recovery of sugar probes (i.e. increased gut integrity), 2) increased fecal SCFA levels; these potentiate intestinal junction protein expression,²⁸ and 3) an alleviation of gut dysbiosis (e.g. microbial diversity, *Firmicutes:Bacteroidetes* ratio). Indeed, we expect reduced gut bacteria abundance. This is important because intestinal bacteria overgrowth provokes metabolic disease.^{37,38} Likewise, MFGM-mediated

prebiotic effects are anticipated to increase commensal bacteria (e.g. butyrate producers) and its anti-microbial activities are expected to reduce pathogenic populations (e.g. pyrogenic bacteria, decreased LPS synthesis).

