
Power Calculation and Data Analysis. [name] (biostatistician; see *Letter of Support*) performed a power analysis using endotoxin (d 14) as the primary outcome. No human studies have examined MFGM on endotoxemia. Thus, we used our data from MetS and healthy persons in which fasting endotoxin was measured 5-times at 2-wk intervals. On average, endotoxin was >2-times higher in MetS ($P<0.0001$), and did not differ ($P>0.4$) by time or gender. We then calculated the mean difference in endotoxin between healthy and MetS subjects (16.4 ± 7.8 vs 32.4 ± 4.4 EU/mL, CV =48% vs 15%). Power analysis indicated that only 8 subjects/group would be required to obtain 95% power ($\alpha = 0.05$) using the larger of the two CVs. For the proposed study in only MetS persons, we estimated that MFGM would result in a conservative improvement of 60% of the difference in endotoxin in the MFGM vs control phases: $((32.4-16.4) \times 0.6 = 9.6$ EU/mL); CV = 32% (SD = 10.4). Thus, we would have ~90% power ($\alpha = 0.05$) with 14 MetS persons completing both study arms. Our targeted enrollment of 24 MetS persons (12F/12M) is therefore expected to be powered strongly to examine MFGM on endotoxemia. This will also account for attrition (estimated at 10%) and provide sufficient power to consider gender x treatment interactions.

Most data will be analyzed by linear mixed effects models with random effect for subjects (to account for repeated measures) and fixed effects for treatment, gender, time period, and their interactions. Multivariate regression will define correlations between variables with consideration of potential covariates. Significance for all analyses will be set at $P<0.05$.

C. Measurement/Instrumentation

Anthropometric Parameters and Blood Pressure. At screening, day 0, 7, and 14, participants will rest for 15 minutes prior to determining blood pressure using an automated cuff. BMI will be calculated from height determined from a wall-mounted stadiometer and weight from a calibrated scale. Waist circumference will be assessed at the level of the umbilicus using a nonflexible measuring tape.

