Microbiota Composition. Microbiota composition will be assessed from fecal samples collected on d 13 of each study period. Samples will be extracted in the [name] lab, and genomic sequencing will be performed in the OSU MCIC core lab (see *Facilities*) using routine procedures. In brief, effects due to MFGM on total bacterial abundance will be assessed using qPCR (i.e. to assess intestinal bacteria overgrowth).⁵⁹ Microbiota of each sample will be characterized for diversity and community structure by sequencing 16S rRNA genes using MiSeq. Bioinformatic analysis will be performed using Qiime⁶⁰ and bacteria identified by comparing each operation taxonomic unit (OTU) to RDP and Silva databases.^{61,62} α -Diversity (OTU richness, Shannon-Wiener diversity index, evenness) will be calculated using Qiime and β -diversity using the Bray-Curtis dissimilarity,⁶³ followed by multivariate analysis (i.e. PCA, PERMANOVA, ANOSIM, PLS-DA) to determine MFGM effects.

The functional metagenome will be predicted using PICRUSt⁶⁴ and PanFP⁶⁵ based on reference databases and the KEGG Orthology classification scheme to obtain a functional gene abundance matrix.

We will validate preclinical findings showing increased microbiota potential to generate SCFAs in response to MFGM.^{30,31,47} These gut health-promoting metabolites (butyrate, acetate, propionate) will be quantified by LC-MS as we described,⁵⁷ with modification,⁶⁶ from fecal samples collected on d 13. Quantification will be performed relative to ¹³C-butyrat, -acetate, or -propionate (internal standards), and normalized to fecal dry matter.

D. Detailed Study Procedures

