Intervention timeline. Each participant will complete a 2-arm (MFGM-Enriched Milk; Coconut/Palm Oil-Enriched Milk), randomized, cross-over study. For this study, each participant will visit the study center a total of 12 times (6 times per study arm, including 1) baseline measurements of anthropometrics, serum glucose, insulin, endotoxin, and pick-up of meals for days 1-3, 2) pick-up of meals for days 4-6, 3) pick-up of meals for days 7-10 and measurement of anthropometrics, 4) pick-up of meals for days 11-14 and stool collection kit, 5) 3 h postprandial testing, and 6) return samples from 24-h urine collection. Interventions will be separated by two weeks (for women, interventions will be separated by 2, 6, 10 etc. weeks to ensure testing will be performed at the same time of the menstrual cycle).

Baseline visit. On day 0 of each trial arm, participants will report in the fasted state (10-12 hours) to the study center for assessment of height, weight, waist circumference, blood pressure, serum glucose, serum insulin, and serum endotoxin. They will receive 3-4 days of meals plus MFGM-enriched milk or coconut/palm oil-enriched milk.

Dietary intervention. Participants will be provided all foods for the 14-d intervention period. After the baseline visit, participants will report back to the study center on days ~6 and 10 to pick up their meals for the proceeding 3-4 days. On day 7, anthropometrics (height, weight, and waist circumference) will also be measured to ensure weight maintenance.

Test trials. At the end of the intervention period (day 14), participants will report back to the laboratory in the fasted state (10-12 hours) for assessment of height, weight, waist circumference, blood pressure, plasma glucose, insulin, gastric inhibitory peptide (GIP), glucagon-like peptide-1 (GLP-1), and serum endotoxin. Participants will return a stool sample collected on day 13 of the intervention period at home. Participants will ingest a sugar solution containing 75 g glucose, which we and others have routinely shown to provoke oxidative stress responses including lipid peroxidation. This will be co-ingested with 1 g sucralose, 1 g erythritol, 5 g lactulose, and 1 g mannitol for assessment of gut permeability. Then, at 30 min intervals during the 3 h postprandial period, we will assess blood markers. During each study visit, participants will have access to drinking water

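### The multivariate microbiota tests do not use the crossover pairing, and the taxon and function comparisons have no multiplicity rule beyond P<0.05

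*Combined protocol and SAP*

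**What the plan says.** The trial is a two-period crossover: "Each participant will complete a 2-arm (MFGM-Enriched Milk; Coconut/Palm Oil-Enriched Milk), randomized, cross-over study" (Section III.D, Intervention timeline). Microbiota come from "fecal samples collected on d 13 of each study period" (Section III.C, Microbiota Composition), so each completer contributes two samples, one per treatment.

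The same section computes Bray-Curtis dissimilarities, "followed by multivariate analysis (i.e. PCA, PERMANOVA, ANOSIM, PLS-DA) to determine MFGM effects". It then predicts the functional metagenome from "reference databases and the KEGG Orthology classification scheme to obtain a functional gene abundance matrix". It does not say how the two samples from one person are linked, and it names no test for individual taxa or genes.

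Section III.B (Power Calculation and Data Analysis) says "Most data will be analyzed by linear mixed effects models with random effect for subjects", with "fixed effects for treatment, gender, time period, and their interactions". It closes with one rule: "Significance for all analyses will be set at $P<0.05". Neither document part gives a multiplicity rule, a number of tests or an exploratory label.

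Comparisons of bacterial groups and functions are nevertheless intended. Under Anticipated Results, the prebiotic effects of MFGM "are anticipated to increase commensal bacteria (e.g. butyrate producers) and its anti-microbial activities are expected to reduce pathogenic populations", with lower LPS synthesis. Under Pitfalls and Alternatives, Gram-negative populations and LPS-biosynthesis functions are to be tested within Objective 1.

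**The concern.** Two separate issues sit in the same analysis, and their effects do not add.

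**Pairing.** A random subject effect in a univariate linear model has no direct counterpart in a permutation test on a distance matrix, in ANOSIM or in PLS-DA. Each needs its own device. If none is used, between-person variation stays in the reference distribution, and the test gives up the main advantage of a crossover. A real shift in community structure could be missed. Pitfalls and Alternatives makes further metagenomic work depend on finding no taxonomic change, so a false null could also misdirect follow-up.

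**Multiplicity.** If endotoxin falls without a change in gut integrity, the plan would attribute this to fewer Gram-negative bacteria or fewer LPS-biosynthesis functions, or else to altered transcellular absorption of LPS. Taxon and function tests at an unadjusted P<0.05 could support the bacterial explanation by chance.

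**Working it through.** **The plan's own figure.** The only power figure is for day-14 endotoxin: about 90% with 14 completers. A two-sided paired t-test with difference 9.6, SD of the within-person difference 10.4 and n = 14 gives 89.1%, so it reproduces. It does so as a within-person analysis. No figure is given for the microbiota.

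**Why plain tests are conservative.** For one feature with variance σ² per period and within-person correlation ρ, the treatment mean difference over n pairs has variance 2σ²(1−ρ)/n. Free permutation without a participant term compares it with a spread of about 2σ²/n. The two agree only at ρ = 0. For ρ > 0 the reference is too wide.

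**Simulated size of the loss.** From the plan: 24 enrolled, 10% attrition, 24 × 0.9 = 21.6, taken as 22 pairs. Assumed, because the documents give none of these: 60 taxa, 12 of them shifted by 0.6 log units, total log-SD 1, and ρ. Bray-Curtis distances, 199 permutations, 800 replicates. Power at 0.05:

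| Method | ρ=0 | 0.2 | 0.35 | 0.5 | 0.8 |
|---|---|---|---|---|---|
| PERMANOVA, pairing ignored | 57% | 41% | 30% | 18% | 2% |
| PERMANOVA, participant fitted, free permutation | 56% | 64% | 75% | 85% | 99.5% |
| PERMANOVA, participant fitted, permuted within participant | 56% | 64% | 76% | 84% | 99.5% |
| PERMANOVA, participant and period fitted, permuted within participant | 55% | 63% | 76% | 85% | 99.5% |
| ANOSIM, free permutation | 55% | 39% | 30% | 19% | 8% |
| ANOSIM, permuted within participant | 55% | 61% | 72% | 82% | 99% |

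With no true effect, the pairing-ignored tests reject about 5% of the time at ρ = 0, under 1% at 0.2 and 0% from 0.35. Every paired version stays between 3.4% and 6.2%. For PERMANOVA the cause is the unmodelled pairing, not free permutation as such (compare rows 1 and 2). ANOSIM takes no covariate, so restricted permutation is its only remedy.

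Other runs at ρ = 0.5 with 22 pairs and different assumed inputs gave 10% to 24.5% with pairing ignored, against 82% to 99% with it used. The direction is stable; the size is not.

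**PLS-DA** (two components, ρ = 0.5). Cross-validated accuracy, where chance is 50%:
- No effect: plain with one sample held out 25%; plain with the pair held out 50%; multilevel with the pair held out 50%; multilevel with one sample held out 93%.
- Shift 0.6: the first three give 67%, 77% and 93%.

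The multilevel form is therefore safe only if both samples of a person are held out together.

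**Multiplicity.** For m independent true-null tests, the chance of at least one false positive is 1 − 0.95^m:
- m = 4: 18.5%; m = 5: 22.6% (about the number of groups that the plan names)
- m = 20: 64%; m = 100: 99% (illustrative counts)

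With features correlated at 0.5 these become 16%, 18%, 44% and 79%.

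The mechanistic argument needs a result in one direction, so the relevant chance is 1 − 0.975^m: 4.9% for two aggregate contrasts, 9.6% for four groups and 11.9% for five.

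**Cost of one large family.** Take a two-sided paired t-test on 22 pairs with 90% power at 0.05 (noncentrality 3.40). If it is the only true signal, Benjamini-Hochberg acts roughly like the threshold 0.05/m. Power falls to about 29% among 100 features and 10% among 1,000. In a family of five (threshold 0.01) it is 71%.

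**The case against.** The strongest reply is that the pairing half rests on silence. The paragraph is a short list of laboratory and bioinformatic methods, PERMANOVA can carry a participant term, and Section III.B shows that the team means to account for repeated measures. Records are coded by participant, so the pairing can still be used at analysis. The harm is conditional and conservative, it concerns secondary outcomes with no power claim, and its simulated size rests on assumed inputs. All of that stands, and it limits the weight of the point.

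It does not remove the point. Whether pairing is used can reverse the result of the community-level test, so the choice should be written down before unblinding. The P<0.05 rule is not silence: it is stated for every analysis.

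Three stronger readings are tempting, and the documents do not support them:
- A reader might infer that two samples per person produce spurious microbiota findings. For PERMANOVA and ANOSIM the error runs the other way, because each person receives both treatments.
- A reader might infer that the plan treats the samples as independent. It does not say so; it omits how they are linked.
- A reader might take 64% or 99% as the chance of falsely supporting the endotoxin mechanism. Those figures count any hit in either direction over assumed numbers of features. The plan gives no feature count, and its mechanism is specific and directional.

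**Conclusion.** The point holds as two limited gaps that should be fixed.

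**Pairing.** As written, PERMANOVA, ANOSIM and PLS-DA have no stated way to use the paired samples. In plain form the first two lose power at any positive within-person correlation: nothing at 0 and most of it at 0.5 under the assumed inputs. The documents give no within-person correlation, so the loss in this trial is unknown. Day-14 endotoxin is unaffected. Diversity indices, the Firmicutes:Bacteroidetes ratio, total abundance and SCFAs also escape, provided they are among the data analysed by the mixed model.

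**Multiplicity.** The flat threshold gives a 19-23% chance of some false positive over 4-5 independent null tests, and more if many features are screened. For the directional claim the chance is smaller: about 5% for two aggregate contrasts and 10-12% for 4-5 groups.

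Confidence is high on the direction of both effects and low on the exact size of the power loss.

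**What to change.** In Section III.C, Microbiota Composition:
- **PERMANOVA:** fit participant and period before treatment, and/or permute treatment labels only within participant. Period is already a fixed effect in Section III.B, if its time-period term means the crossover period.
- **ANOSIM:** permute only within participant, or drop it.
- **PLS-DA:** use the multilevel (within-participant) form, validated by holding out both samples of a participant together.
- **Named contrasts:** list in advance the few hypothesis-driven comparisons, for example Gram-negative abundance, LPS-biosynthesis functions and butyrate producers. Make them a small family of their own with a stated multiplicity adjustment.
- **Everything else:** analyse the remaining taxa (at a stated rank) and KEGG functions with the Section III.B mixed model after a stated transformation suited to relative abundances. Apply Benjamini-Hochberg control at 5% within each family and label the results exploratory.

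In Section III.B, exempt these families from the plain P<0.05 rule.

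The cost is a few sentences and some analysis settings, with no new data. Pairing costs essentially no power at correlation 0 (56% against 57%), and adding period costs none at 0.5 (85% against 84%). The real downside is that fewer individual taxa or functions will be called significant. Keeping the named contrasts out of the large KEGG family prevents the fall to 29% or 10% power shown above.
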